#### **Statistical Methods:**

We reported that the average IEFND in the distal leg in T1DM subjects (mean disease duration of 27 years) was 2.2 fibers/mm. We assume that the targeted diabetic subjects have the average IENFD for ages 20-29 shown by published normatives at the start of their disease, and the decline due to diabetes is 10 fibers/mm or an average of 0.25 fibers/mm/year. If the decline is more rapid as neuropathy progresses, then the average decline in IEFND may be as high as 0.5 fibers/mm/year. Based on our assumption about the mechanism by which salsalate will influence IEFND (reduction of inflammation), and published effect of other interventions, we believe that an increase of 1.65 fibers/mm (0.25 + 1.4 = 1.65) in fiber density is possible with treatment with salsalate. The standard deviation

of the change is approximately 2 fibers/mm. With 25 subjects per group there will be 81% power to reject the null hypothesis of no difference between groups using a two-tailed t-test at a 5% level of significance. No formal interim analysis for stopping for efficacy benefit or futility is planned, given the projected duration of follow-up required for the assessment of the primary endpoint. Rather, safety will be assessed periodically and reviewed by a Data and Safety Monitoring Board.

A general linear model will be fitted to the change in IENFD score with factors for treatment group, baseline HbA1c ( $\leq 8.0$  or  $> 8.0\%$ ), and baseline IEFND as fixed covariates. If the distributional assumptions are not met, transformations of IENFD or the use of nonparametric methods will be employed. Sensitivity analyses will be performed to assess how subjects who withdrew may affect conclusions of the analysis. An intent-to-treat analysis set (including subjects who are randomized, treated and have a baseline IENFD) will be used to assess treatment effects with multiple imputation methods employed to impute outcomes for subjects with missing post-baseline data.

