#### **10.1. Sample Size Determination**

The purpose of this clinical trial is to provide the preliminary data necessary to design a larger

multi-site clinical trial. There are two assumptions that are necessary to justify the larger trial. The first is that salsalate will cause an increase in nerve fiber density (re-innervation) and the second is that the natural progression of DN, even with treatment for diabetes, leads to loss of nerve fibers. The primary outcome is an assessment of IENFD at the distal thigh after 12 months of placebo or salsalate treatment.

In the largest study of IENFD, Lauria et al provided a table of median IEFND values in the distal leg as a function of age and gender. In the 20-29 age range the average IEFND was 12.2 fibers/mm with an average decline of 0.1 fibers/mm per year. We reported that the average IEFND in the distal leg in T1DM subjects (mean disease duration of 27 years) was 2.2 fibers/mm. If we assume that our diabetic subjects have the average IENFD for ages 20-29 shown by Lauria et al at the start of their disease, then the decline due to diabetes was 10 fibers/mm or an average of 0.25 fibers/mm /year. If the decline is more rapid as neuropathy progresses, then the average decline in IEFND may be as high as 0.5 fibers/mm/year.

In a study of the effect of physical exercise Smith et al found an increase in the IENFD at the thigh of 1.4 fibers/mm after one year of intervention. Based on our assumption about the mechanism by which salsalate will influence IEFND (reduction of inflammation), we believe that a similar increase in fiber density is possible with treatment with salsalate. In multiple studies that reported a change in IEFND over time (including one of our own studies), the standard deviation of the change was approximately 2 fibers/mm. With the above assumptions, there will be an expected difference of 1.65 fibers/mm ( $0.25 + 1.4 = 1.65$ ) in the change between the two groups at the thigh with a standard deviation of 2.0. With 25 subjects per group there will be 81% power to reject the null hypothesis of no difference between groups using a two-tailed t-test at a 5% level of significance. Prior data are insufficient to perform a power calculation for the distal leg.

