The trial will be considered a success if the primary endpoint demonstrates a significant difference between the two groups and one other secondary endpoint trends in a similar direction. This trial will also be considered a success if there is sufficient evidence to show that IEFND increases with salsalate but is likely to decrease with usual treatment. With 25 subjects per group, the standard error of the estimate will be approximately 0.4 [=2/square root (25)] and therefore the confidence interval for the mean change in each group will be the estimated mean change  $\pm$  0.8 fibers/mm; i.e. an increase of greater than 0.8 fibers/mm with salsalate and an observed decrease with placebo (since the expected decrease with placebo is not expected to be large). With these results, this trial would provide the preliminary data needed for a larger trial to validate the effect of salsalate. Assuming 15-20% attrition rates, 70 subjects will be recruited to attain the necessary 50.

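### The sample-size figures in Section 10.1 still describe 50 completers at 1:1; at 15-20% attrition, 70 recruits leave 56-59, and power is about 84-87% rather than the stated 81%

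*Combined protocol and SAP*

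**What the plan says.** Section 10.1 assumes a between-group difference of 1.65 fibers/mm in the change in IENFD, a standard deviation of 2.0 and a two-sided 5% t-test. It concludes: "With 25 subjects per group there will be 81% power to reject the null hypothesis of no difference between groups". On precision it says: "With 25 subjects per group, the standard error of the estimate will be approximately 0.4", and from that it takes ±0.8 fibers/mm for the mean change in each group. It then illustrates its second route to success as "an increase of greater than 0.8 fibers/mm with salsalate and an observed decrease with placebo". It closes with the recruitment number: "Assuming 15-20% attrition rates, 70 subjects will be recruited to attain the necessary 50".

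Under Statistical Methods, the synopsis repeats only the power statement ("With 25 subjects per group there will be 81% power to reject the null hypothesis"). The attrition sentence and the ±0.8 are not in the synopsis.

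The synopsis design paragraph and Section 3 describe a different trial: 70 subjects at 3:2. Section 3 explains that the plan was first for up to 60 subjects at 1:1. In August 2017, on the DSMB's recommendation, this became up to 70. The stated reasons were unequal discontinuation of study medication and a wish to expose more subjects to salsalate. The 3:2 ratio applies to subjects enrolled after the revised protocol was approved.

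**The concern.** The recruitment sentence presents 70 as the number that yields 50 at 15-20% attrition, and it is not. The power and precision statements rest on equal arms of 25, while the trial allocates unequally and recruits more. The section therefore does not give the expected completers, power or per-arm precision of the trial being run.

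Two things depend on this. Section 10.1 says the trial exists to supply preliminary data for a larger one, so its planners may reuse these attrition and precision figures. The section also ties an illustrated success criterion to per-arm precision, and the salsalate arm is no longer expected to have 25 completers.

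**Working it through.** **Inputs.** Section 10.1: difference 1.65, SD 2.0, two-sided 5% t-test, 25 per group, attrition 15-20%, 70 recruited, 50 needed. Section 3: formerly 60 at 1:1, now 70, with 3:2 for later enrollees.

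**1. The plan's own power and precision.** Noncentrality = 1.65 / (2 × √(1/25 + 1/25)) = 1.65 / 0.566 = 2.92 on 48 degrees of freedom. Power from the noncentral t distribution is 0.815, which agrees with the stated 81%. SE = 2/√25 = 0.4, and two SEs give ±0.8. Both figures reproduce, for 25/25.

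**2. The attrition sentence.**
- Forward from 70: 70 × 0.80 = 56 and 70 × 0.85 = 59.5, so 56-59 whole subjects.
- Backward from 50: 50/0.85 = 58.8 and 50/0.80 = 62.5, so 59-63 recruits. The cruder inflation 50 × (1 + rate) gives 58-60. Neither method gives 70.
- Attrition implied by 70 to 50: 1 − 50/70 = 28.6%.
- Forward from the former 60: 60 × 0.80 = 48 and 60 × 0.85 = 51. The sentence works for 60.

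**3. Power and precision for the present design.** Same difference, SD and test; expected completers left fractional; half-width = 2 × 2/√n, as in the plan. The documents do not say how many subjects were randomized 1:1 before the revision, so that count is an assumption, as are the attrition rates by arm.

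| Scenario (salsalate/placebo randomized) | Attrition | Completers | Power | Half-widths |
|---|---|---|---|---|
| All 70 at 3:2 (42/28) | 20% each | 33.6/22.4 | 0.844 | ±0.69 / ±0.85 |
| All 70 at 3:2 (42/28) | 15% each | 35.7/23.8 | 0.866 | ±0.67 / ±0.82 |
| All 70 at 3:2 (42/28) | 25% / 10% | 31.5/25.2 | 0.858 | ±0.71 / ±0.80 |
| 20 early at 1:1 (40/30) | 20% each | 32.0/24.0 | 0.851 | ±0.71 / ±0.82 |
| 20 early at 1:1 (40/30) | 15% each | 34.0/25.5 | 0.872 | ±0.69 / ±0.79 |
| 30 early at 1:1 (39/31) | 20% each | 31.2/24.8 | 0.854 | ±0.72 / ±0.80 |
| 30 early at 1:1 (39/31) | 15% each | 33.15/26.35 | 0.875 | ±0.69 / ±0.78 |
| Exactly 50 completers at 3:2 | 28.6% each | 30/20 | 0.800 | ±0.73 / ±0.89 |

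**4. Could 70 have been chosen so that unequal loss leaves 25/25?** From 42/28 that needs a loss of 1 − 25/42 = 40.5% on salsalate and 1 − 25/28 = 10.7% on placebo. The overall loss is again 28.6%, outside the stated 15-20%.

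**The case against.** The strongest reply is that nothing of substance follows. At the stated attrition every scenario gives 84-87% power, above the 81% claimed. The placebo half-width of 0.82-0.85 under full 3:2 allocation still rounds to the stated 0.8, and the salsalate arm is more precise than stated. If 20-30 subjects entered at 1:1, 24-26 placebo completers are expected, so 25 is close for that arm. All of this stands and keeps the point minor. It does not make the attrition sentence true, nor does it make 25 per group a description of arms expected to be about 31-36 and 22-26.

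It can also be said that the reason for 70 is on record. That stands too: Section 3 gives it. The remaining conflict is that Section 10.1 attributes 70 to attrition, which its own rates do not support.

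A reader might go further in three ways that the documents do not support.
- **That the trial is underpowered.** Even 50 completers split 30/20 give 80.0%.
- **That unequal discontinuation means unequal loss of month-12 biopsies.** Section 5.2.4 keeps subjects in follow-up on the intention-to-treat model, so stopping tablets need not mean a missing outcome.
- **That the effect size is unsound, because "the decline due to diabetes was 10 fibers/mm or an average of 0.25 fibers/mm" per year does not follow from a mean duration of 27 years.** Indeed 10/27 = 0.37 per year, or 0.27 after subtracting the section's own ageing decline of 0.1 per year. But 0.25 is below both and so conservative. Using 0.27 makes the difference 1.67 and power at 25/25 0.825; using 0.37 gives 1.77 and 0.866. The section itself allows a decline of up to 0.5. This is a separate matter, and at most the derivation could be shown.

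**Conclusion.** The point holds as a minor but real error in the sample-size justification. The attrition sentence is arithmetically wrong as it stands, and this needs no assumption: 56-59 completers, not 50. The likeliest cause is that 60 became 70 without recalculation, since the sentence works for 60. That is an inference from the numbers; the documents do not say so.

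The power and precision figures are correct for 25/25 but do not describe the design in force. For that design the best available statement is 84-87% power. It rests on the plan's difference of 1.65 and SD of 2.0, on 15-20% attrition in each arm, and on either full 3:2 allocation or 20-30 early subjects at 1:1.

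One consequence should be settled. Section 10.1 derives the 0.8 from n = 25, so it is unclear whether 0.8 is a fixed threshold or an illustration of the salsalate interval excluding zero. With 34-36 salsalate completers the two readings differ for an observed mean increase between about 0.67-0.69 and 0.8.

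**What to change.** In Section 10.1:
- Correct the attrition sentence. Either state that 70 recruits at 15-20% attrition are expected to leave 56-59 completers, or state the attrition rate that justifies 70 for 50 (28.6%). Give the Section 3 reason for choosing 70.
- Replace the equal-arm figures with expected completers, power and interval half-width by arm under the allocation actually used. Take the number randomized 1:1 from the trial's records, and use arm-specific attrition if the sponsor expects it to differ.
- State, before unblinding, whether the 0.8 fibers/mm is kept as a fixed value or whether the criterion is that the salsalate-arm confidence interval excludes zero. Section 10 provides for a statistical analysis plan to be finalized before the blind is broken, so the statement can go there as well.
- Optionally, show how 0.25 per year was obtained.

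In the synopsis, update only the 25-per-group, 81% statement.

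The cost is a few sentences and one small table. No subjects are added, and enrolment, allocation, endpoint and primary analysis are unchanged.

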## 10.2. Efficacy Analysis

*The two treatment groups will be compared with respect to demographic and baseline variables (e.g., age, BMI, smoking, etc.). If a significant difference is found in any variable, the models described below will be fitted both with and without the variables that differ at baseline.*

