### Analysis of Primary Outcome:

The primary outcome is change from baseline to 12 months in IENFD at the distal thigh. A general linear model will be fitted to the change in IENFD score with factors for treatment group, baseline HbA1c ( $\leq 8.0\%$  or  $> 8.0\%$ ), and baseline IEFND as fixed covariates. If the distributional

assumptions are not met, transformations of IENFD or the use of nonparametric methods will be employed. Sensitivity analyses will be performed to assess how subjects who withdrew may affect conclusions of the analysis. An intent-to-treat analysis set (including subjects who are randomized, treated and have a baseline IENFD) will be used to assess treatment effects with multiple imputation methods employed to impute outcomes for subjects with missing post-baseline data. Depending on the extent and pattern of missingness, other simpler sensitivity analyses may be used: for example, change from baseline to month 12 for subjects completing the study (completers) may be analyzed using an analysis of variance model. The model will include the same covariates that are included in the primary analysis.

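### Baseline significance tests choose the covariates for a second version of the primary model, and no section says that the pre-specified version alone decides success.

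*Combined protocol and SAP*

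**What the plan says.** Section 10.2 (Efficacy Analysis) opens with a rule that governs everything after it: "The two treatment groups will be compared with respect to demographic and baseline variables (e.g., age, BMI, smoking, etc" and so on, an open list. Then: "If a significant difference is found in any variable, the models described below will be fitted both with and without the variables". The variables meant are those flagged by the comparison. No significance level is given for these tests.

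The first model below that rule is the primary one, under Analysis of Primary Outcome: "A general linear model will be fitted to the change in IENFD score with factors for treatment group", baseline HbA1c stratum and baseline IENFD. The Synopsis repeats this model.

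Section 10.1 states: "The trial will be considered a success if the primary endpoint demonstrates a significant difference between the two groups" and one secondary endpoint trends the same way. It does not say which version of the model supplies the significant difference. It also gives a second route to success, based on the change within each group.

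Section 3 stratifies randomisation by HbA1c and by gender within HbA1c group. Section 5.1 and the Synopsis mention HbA1c only, and gender is not in the primary model. The opening of Section 10 defers detail to a Statistical Analysis Plan to be finalised before the blind is broken; no separate text of it is in the documents.

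**The concern.** There are two linked weaknesses.

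- **The selection rule.** When allocation is random, any baseline difference is a chance difference, and its p-value says nothing about whether the variable predicts change in IENFD. In a trial of this size the test passes over moderate imbalance in a strong predictor and flags irrelevant variables at its nominal rate.
- **The decision rule.** The rule can produce two results for the primary endpoint. If one is below 0.05 and the other above, the first success criterion in 10.1 has no defined answer. Whoever settles it would do so after seeing both p-values.

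**Working it through.** **1. The plan's own figure.** Inputs from 10.1: "With 25 subjects per group there will be 81% power to reject the null hypothesis of no difference between groups"; "there will be an expected difference of 1.65 fibers/mm"; SD 2.0; "two-tailed t-test at a 5% level of significance". Noncentrality = 1.65 / (2.0 × √(1/25 + 1/25)) = 1.65 / 0.566 = 2.92 on 48 degrees of freedom. Power is 81.5%, which agrees with the stated 81%.

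**2. What the baseline test can detect.** Section 10.1 needs 50 evaluable subjects; at 3:2 that is about 30 and 20 (an approximation, since early subjects were allocated 1:1). A two-sided 5% t-test flags an observed difference only above 2.01 × √(1/30 + 1/20) = 2.01 × 0.289 = 0.58 SD. The baseline comparison could use all 70 randomised subjects, about 42 and 28: 2.00 × √(1/42 + 1/28) = 2.00 × 0.244 = 0.49 SD. Either way, an imbalance of up to about half an SD is ignored, however prognostic the variable.

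**3. How often a second version arises.** The number of variables (k), their independence and the 5% level are assumptions. The chance of at least one significant difference is 1 − 0.95^k.

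| k | Chance |
|---|---|
| 3 | 14% |
| 5 | 23% |
| 10 | 40% |
| 15 | 54% |
| 20 | 64% |

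Correlation lowers these. With pairwise correlation 0.3, simulation gives about 36% for 10 variables and 45% for 15.

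**4. Type I error.** Simulation with no treatment effect: 20,000 trials per row, 30 against 20 subjects with complete data. The base model has treatment, HbA1c stratum and baseline IENFD; any baseline variable with p < 0.05 is added in the second version. R² is the assumed share of outcome variance that the tested variables explain.

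| k | R² | Second version arises | Pre-specified model decides | Adjusted version decides when it arises | Either may decide |
|---|---|---|---|---|---|
| 5 | 0 | 22.8% | 4.9% | 5.0% | 5.3% |
| 5 | 0.3 | 22.5% | 4.9% | 4.2% | 5.3% |
| 10 | 0 | 39.8% | 4.9% | 4.9% | 5.7% |
| 10 | 0.3 | 40.0% | 5.1% | 4.3% | 5.7% |
| 10 | 0.5 | 40.5% | 4.9% | 3.6% | 5.6% |

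Simulation error is about 0.2 points. Further simulations with 3 to 15 variables put the either-version error at about 5% to 6.5%.

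Among only those trials in which a second version arises, the either-version error is 6.6% to 9.6%. In those same trials the pre-specified model alone rejects in 4.7% to 7.7%, so the freedom to choose adds 1.5 to 2.0 points there.

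**5. How often the versions disagree.** At the design effect (1.65 / 2.0 = 0.825 SD), with 10 variables explaining 0 to 25% of outcome variance, the two versions fall on opposite sides of 0.05 in about 12% to 15% of triggered trials. With a second version in about 40% of trials, that is 0.40 × 0.12 = 5% to 0.40 × 0.15 = 6% of all trials.

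**The case against.** The strongest reply is that the plan does have a primary model. Section 10.2 sets it out under its own heading with a fixed covariate list, and the completer analysis is told to use the covariates of the primary analysis, which presupposes a single one. The version without the flagged variables is exactly that model, and fitting both can be read as a robustness check reported openly. This largely stands: the plan does not leave two equal candidates. But it is an inference. The baseline rule comes before the primary model and modifies it, and reporting both results does not say which one counts.

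A reader might infer that the sponsor may pick the better p-value and that type I error is materially inflated. No section permits that choice. Even if it were allowed, the excess is small, and it vanishes if either version is fixed in advance as decisive.

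A reader might also infer that precision from known predictors is gained only when a baseline test happens to be significant. That is not so. Baseline IENFD and HbA1c stratum are always in the primary model, and the secondary analyses explore age, sex, BMI, smoking and other covariates whatever the baseline tests show.

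Two points lower the stakes. Section 10.1 says the trial is to supply preliminary data for a larger one and offers a success route that needs no between-group p-value. The separate Statistical Analysis Plan may already settle the matter, which cannot be checked here.

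**Conclusion.** The point holds in limited form. Baseline significance tests are an unsound way to choose covariates in a randomised trial, and the implied primary model is never named as the sole basis for the criterion that "the primary endpoint demonstrates a significant difference between the two groups". The practical harm is an undefined conclusion when the versions disagree: about 5% to 6% of all trials at the design effect with 10 tested variables. Error inflation is slight, to about 5% to 6.5% and only if either version could claim success.

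These sizes rest on assumptions that the documents do not supply: the number of variables, their independence, a 5% baseline test, their prognostic strength, and complete data on 30 and 20 subjects. The trigger probability in particular should be read as a range of 14% to 64%. The criticism of the selection rule and the missing decision rule do not depend on these figures.

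**What to change.** - In 10.2, replace the baseline-test rule: summarise demographic and baseline variables by arm, without significance tests.
- In 10.1 and 10.2, state that one pre-specified model (treatment, baseline IENFD, HbA1c stratum and gender) alone decides whether the primary endpoint meets the success criterion. Gender is added because Section 3 stratifies by it. This is a related but separate repair, and Section 5.1 and the Synopsis should be brought into line with Section 3.
- If a further adjusted model is wanted, fix its covariate list before unblinding, choose the variables for expected prognostic value, and label the model a sensitivity analysis that cannot change the success decision.
- Carry the same wording into the Synopsis and the Statistical Analysis Plan.

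The cost is wording, plus one degree of freedom for gender. No new data are needed, since gender is already used at randomisation.

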### Analysis of Primary Outcome:

The primary outcome is change from baseline to 12 months in IENFD at the distal thigh. A general linear model will be fitted to the change in IENFD score with factors for treatment group, baseline HbA1c ( $\leq 8.0\%$  or  $> 8.0\%$ ), and baseline IEFND as fixed covariates. If the distributional

assumptions are not met, transformations of IENFD or the use of nonparametric methods will be employed. Sensitivity analyses will be performed to assess how subjects who withdrew may affect conclusions of the analysis. An intent-to-treat analysis set (including subjects who are randomized, treated and have a baseline IENFD) will be used to assess treatment effects with multiple imputation methods employed to impute outcomes for subjects with missing post-baseline data. Depending on the extent and pattern of missingness, other simpler sensitivity analyses may be used: for example, change from baseline to month 12 for subjects completing the study (completers) may be analyzed using an analysis of variance model. The model will include the same covariates that are included in the primary analysis.

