**Trial Design:** This is a phase II-III, multi-site randomized, double-blind, placebo-controlled clinical trial to evaluate the effect of salsalate on measures of small fiber neuropathy in 70 subjects with T1DM and mild DN. Subjects will be randomized in a 3:2 fashion to (up to) 3 grams/day salsalate or matched placebo and receive study medication for 12 months. Randomization will be stratified by baseline HbA1c (( $\leq$ 8.0 or  $>$ 8.0%)). Subjects will be evaluated every 3 months for a total of 12 months.

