## SUMMARY OF CHANGES:

Protocol Version 1.2  
July 13, 2016:

Section 4.1 Exclusion Criteria: Updated to allow continued low-dose (81 mg daily) aspirin therapy.

Section 2, 6.1, 6.2, Table 1: Updated to move quantitative sensory testing to the screening visit, rather than baseline visit.

Section 2: Corrected to indicate that nerve conduction studies are done at the screening visit.

Section 2, 4.1, 6.1, 7.1.2: Updated to indicate that the ulnar nerve will be tested, rather than median nerve.

Protocol Version 1.3  
October 19th, 2016:

Table 1: Proposed visit schedule corrected for spelling and timing of events.

Section 1 & 10.1: Corrected to indicate that this is a single center (not multi-center) study.

Section 4.1: Added history of keloid scarring to list of exclusions.

Section 6.2: Removed language related to subject medication log

Section 10.6: Added reference that MICHR will provide study monitoring.

Throughout protocol provided clarification that research pharmacy used is Belmar Pharmacy (not UMHS Research Pharmacy).

Minor typographical, spelling and grammatical errors fixed throughout.

Protocol Version 1.4  
December 6th 2016

Section 3: Added that randomization will be by gender as well as by HbA1c.

Section 4.1: Clarified inclusion and exclusion criteria as follows;

-Severe hypoglycemia is defined by hypoglycemia resulting in coma or seizure.

-Active Hepatitis C is an exclusion.

-Active foot ulcers are an exclusion.

-Exclusion related to DKA clarified to a history of recurrent DKA or any DKA in the prior 3 months.

-Lithium use added to list of exclusions

-Upper age for eligibility increased from 65 to 70 years.

Protocol Version 1.5  
February 28, 2017

Section 4.1: Inclusion criteria amended follows;

-Inclusion criteria # 4 amended to include provision to use peroneal motor nerve conduction velocity of  $\geq 35$  m/second as inclusion criteria if sural nerve amplitude is 0  $\mu$ V (unrecordable).

Section 4.1: Clarified exclusion criteria as follows;

-Exclusion # 9 clarified with addition of chronic immunosuppressive therapy to long-term glucocorticoid therapy, exception specified for those using steroid inhalers for asthma management.

-Exclusion # 15 corrected to reflect treatment period of 12 months rather than 24 months.

-Exclusion # 16 added (exclusions related to hypersensitivity to salsalate, aspirin and other NSAIDS). Language related to hypersensitivity is

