### 3. TRIAL DESIGN

This is a phase II-III, multi-site randomized, double-blind, placebo-controlled clinical trial to evaluate the effect of salsalate on measures of small fiber neuropathy in 70 subjects with T1DM and mild DN. In the original study design we proposed to randomize up to 60 subjects in a 1:1 fashion to up to 3 grams of salsalate or matched placebo. In August 2017 the protocol was modified by recommendation of the DSMB to address differential study medication discontinuation rates and to increase the number of subjects exposed to study drug. Specifically, the protocol will enroll up to 70 subjects and randomize them in a 3:2 fashion to

salsalate or placebo. All subjects enrolled subsequent to the approval of the revised protocol will be randomized in 3:2 fashion, up to 3 grams per day of salsalate or placebo respectively. Treatment duration will be 12 months. Randomization will be stratified by baseline HbA1c ( $\leq 8.0$  or  $> 8.0\%$ ) and by gender within the HbA1c groups. Subjects will be evaluated every 3 months for a total of 12 months.

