## 5. TRIAL TREATMENTS

### 5.1. Allocation to Treatment

Randomization to Salsalate or Placebo: After signing informed consent, confirming eligibility and completion of baseline assessments (visit 2), subjects will be randomized to salsalate, up to 3 grams/daily or matched placebo for 12 months. Randomization will be stratified by baseline HbA1c ( $\leq 8.0\%$  or  $> 8.0\%$ ).

Procedure for Subject Treatment Assignment: Subjects will be randomized to treatment with either Salsalate or Placebo. The procedures for randomization will be determined by the study biostatistician.

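### Randomisation is stratified by gender within HbA1c, but the primary model does not pre-specify gender; adding it is a modest, nearly free improvement

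*Combined protocol and SAP*

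**What the plan says.** **Randomisation.** Section 3 (Trial Design) stratifies by baseline HbA1c (at or below 8.0%, or above) "and by gender within the" HbA1c groups, which makes four strata. The Summary of Changes entry for version 1.4 shows that this was deliberate: "Added that randomization will be by gender as well as by HbA1c". Two other places name HbA1c alone: the Synopsis under Trial Design ("Randomization will be stratified by baseline" HbA1c) and Section 5.1 ("Randomization will be stratified by baseline HbA1c").

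**Primary model.** Section 10.2 states: "A general linear model will be fitted to the change in IENFD score with factors for treatment group, baseline HbA1c". The Synopsis repeats this model, and both texts end the covariate list with baseline IENFD ("and baseline IEFND as fixed covariates"). There is no gender term. The completers sensitivity analysis inherits the omission: "The model will include the same covariates that are included in the primary analysis". The imputation model is not specified.

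**Other routes for gender.** Section 10.2 opens with a rule based on baseline tests: "If a significant difference is found in any variable, the models described below will be fitted both with and without" those variables. Under the secondary outcomes, sex is one of several candidates in an exploratory forward stepwise search with p < 0.10 for retention. Section 10 leaves detailed methods to a statistical analysis plan to be finalised before the blind is broken.

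**The concern.** The plan adjusts for one stratification factor and drops the other without giving a reason. Stratification balances gender between the arms. If gender is related to the 12-month change, that balance lowers the true variance of the treatment estimate. A model without gender leaves the gender variance in the residual, so the reported standard error does not show the reduction. The confidence interval is then too wide and the actual type I error falls below 5%.

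At stake is a little power in a trial planned at 81% with 25 per group. The validity of the estimate is not in question.

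Neither of the other routes replaces pre-specification. The baseline rule depends on an imbalance that stratification is designed to prevent, and the stepwise search is data-driven. The later analysis plan may include gender, but nothing in this document commits to it.

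Separately, the document contradicts itself on how subjects are randomised, and the model in Section 10.2 matches the shorter description.

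**Working it through.** **The plan's own figure.** Section 10.1 gives difference 1.65, SD 2.0, 25 per group and a two-sided 5% t-test. SE = 2 × √(2/25) = 0.566; noncentrality = 1.65/0.566 = 2.917; critical t on 48 df = 2.011. Power is 81.5%, which agrees with the stated 81%.

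**Inputs for the comparison**
- From the documents: 70 randomised; 20% attrition (upper end of 15-20%, Section 10.1), hence 70 × 0.8 = 56 evaluable; difference 1.65; SD 2.
- Assumed: 20 of the 70 entered at 1:1 before the change to 3:2. That gives 10 + 30 = 40 on salsalate and 10 + 20 = 30 on placebo, or 32/24 after 20% attrition.
- Assumed: the share R² of the variance in change that gender explains, from 0 to 10%. The documents give no figure.

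**Formulas** (exact gender balance between arms)
- SE₀ = 2 × √(1/32 + 1/24) = 0.540.
- Planned model: reported SE 0.540, true SE 0.540 × √(1 − R²), 52 df, critical t 2.007.
- With gender: reported and true SE both 0.540 × √(1 − R²), 51 df, critical t 2.008.
- Power from the noncentral t with noncentrality 1.65 / [0.540 × √(1 − R²)]. For the planned model the effective critical value is 2.007 / √(1 − R²).
- Example at R² = 5%: effective critical value 2.007/√0.95 = 2.059, so actual alpha is 4.45%. With gender, the 95% CI half-width is 2.008 × 0.540 × √0.95 = 1.057 fibers/mm.

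| R² | Alpha, planned | Power, planned | Power, with gender | Change (points) | CI half-width, planned → with gender |
|---|---|---|---|---|---|
| 0% | 5.0% | 85.04% | 85.02% | -0.03 | 1.084 → 1.084 |
| 1% | 4.9% | 85.16% | 85.37% | +0.2 | 1.084 → 1.079 |
| 5% | 4.5% | 85.64% | 86.76% | +1.1 | 1.084 → 1.057 |
| 10% | 3.9% | 86.26% | 88.48% | +2.2 | 1.084 → 1.029 |

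Break-even is at R² = 0.1%. The split hardly matters: at R² = 5% and 10% the change is +1.1 and +2.3 at 33/23, +1.1 and +2.2 at 31/25, and +1.3 and +2.6 at 25/25.

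**What these R² values mean.** With a 50/50 gender split and SD 2, R² = gap²/16, where gap is the male-female difference in 12-month change. R² of 1%, 5% and 10% corresponds to gaps of 0.40, 0.89 and 1.26 fibers/mm.

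**Simulation** (10,000 trials per setting; assumed blocks of 4 then 5 and 50/50 gender and HbA1c). Change in power, in points, at R² = 0, 1, 5 and 10%:
- Multiple imputation of all 70, 20% random dropout: -0.3, 0.0, +1.4, +2.9 (Monte Carlo error of the difference 0.2). Planned-model alpha: 4.7%, 5.1%, 4.4%, 4.3%.
- Completers in the same trials: -0.1, 0.0, +1.1, +2.7.
- Completers with differential dropout (25% salsalate, 13% placebo): -0.3, -0.1, +1.4, +2.1.
- If baseline IENFD correlates 0.3 with gender, the gain at 5% is +0.9.

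**Would the baseline rule bring gender in?** Gender differed between arms at p < 0.05 in none of the simulated trials when every subject was stratified by gender, and in 0.2% when the first 20 were not.

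**The case against.** The strongest objection is that the larger gains need gender effects that look implausible beside the plan's own numbers. Section 10.1 expects a decline of 0.25 fibers/mm per year, at most 0.5, and a treatment difference of 1.65. R² of 5% needs a gender gap of 0.89, about 3.5 times the expected yearly decline. R² of 10% needs 1.26, or 76% of the whole treatment effect. A gap of 0.25 gives R² = 0.25²/16 = 0.4% and a gain of 0.06 points; a gap of 0.5 gives 1.6% and about 0.3 points. The only gender link in the document concerns IENFD level in normative data, and baseline IENFD is already in the model. Around R² of 0 to 1% the simulations show no gain, and under multiple imputation the conservatism at 10% is milder (alpha 4.3%, not 3.9%). The trial is meant to supply preliminary data, and the later analysis plan may already cover the point.

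Most of this stands as a limit on size: on values tied to the document, the expected gain is a few tenths of a point at most. It does not remove the point. Section 10.1 does not rule out larger gaps, for example if men and women respond differently to treatment. The downside is equally small, and deferral to a later plan does not change the model stated here. It is also fair that the documents do not show which randomisation scheme was actually run, so that should be confirmed when the text is aligned.

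**Conclusion.** The point holds as a recommended, low-stakes change. Section 3 stratifies by gender within HbA1c, the stated primary model omits gender, and no other provision pre-specifies it. The omission causes no bias and no excess false positives; it can only make the test conservative. By formula at 32/24, including gender is worth +0.2 to +2.2 points of power if it explains 1% to 10% of the variance in change, and costs 0.03 points if it explains none (0.1 to 0.3 in simulation, where dropout leaves gender slightly unbalanced). The gain depends on a gender effect that the documents do not quantify. The 32/24 split, the block sizes and the 50/50 gender and HbA1c mix are also assumptions. The disagreement over stratification factors between Section 3, Section 5.1 and the Synopsis needs correcting whatever the gain in power; the version 1.4 entry suggests that the two shorter texts were not updated.

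**What to change.** - In Section 10.2, or in the statistical analysis plan before unblinding, add gender as a fixed effect to the primary model, the multiple-imputation model and the completers analysis. Make the same change to the model in the Synopsis.
- Confirm from the randomisation specification that gender strata are in use, then add gender to the stratification factors in the Synopsis (Trial Design) and Section 5.1 so that they agree with Section 3.
- No primary-model term for the allocation phase (before or after the change from 1:1 to 3:2) is requested; it is at most an optional sensitivity analysis.

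The cost is one model term (52 to 51 residual degrees of freedom at 56 evaluable) and some wording. No new data are needed, because gender has to be recorded in order to stratify by it.
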